21 July 2020	Amendment 3	

• Addition of Study Period 3 to assess the safety and efficacy of long-term treatment with IgPro20 for DM.

• Addition of safety, efficacy, and exploratory endpoints associated with the addition of Study Period 3

• Modified stopping rules and monitoring related to TEEs

• Adjusted language in blinding procedures to account for Period 3

• Added detail to contraindications

• Clarified lifestyle restrictions with relation to physiotherapy

• Adjusted the Study Procedures and Visit Schedule for Study Period 3

• Adjusted language for blood and PK sample collection

• Minor corrections and clarifications, including word modifications and administrative changes

--------------	-------------	--

20 Oct 2022	Amendment 4	

1. Updated Screening assessments

2. Clarified the previous “primary analysis” designation as either “primary data analysis” or “primary endpoint analysis”

3. Defined that 3 data analyses will be performed, and defined the EOP1 analysis as the primary data analysis

4. Removed references to which data are intended to be used for marketing authorization application

5. Updated study unblinding procedures

6. Clarified conditions of concomitant oral corticosteroid taper after Week 17

7. Specified that doses of stable concomitant medication may be decreased during Study Period 3 based on subject status

8. Clarified definitions for reference visits and end of period

9. Clarified statistical methods

10. Corrected minor errors concerning statistical analyses

11. Updated the weight-based dosing regimen table

12. Updated that rate of TEAEs per time at risk will be calculated instead of TEAEs per days with infusion

13. Update primary and key secondary estimands and statistical methods to account for intercurrent events of withdrawals related to the Ukraine war and add a sensitivity analysis for the primary estimand.

14. Extend the study open-label period, Study Period 3, until <del>CC1</del> months <del>CC1</del> [REDACTED] [REDACTED] for the indication Dermatomyositis, whichever comes first

-------------	-------------	---

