studies have been conducted and are summarized in a systematic review [Wang et al, 2012]. Clinical improvement was reported in up to 93% of subjects in early and therapy-refractory DM/PM; the typical dose was 2 g/kg IVIG given over 3 to 6 months. It has been reported that long-term use of IgG therapy is safe and effective, but this has not yet been confirmed in clinical studies. In a retrospective long-term study, 42 subjects with DM were followed; 24 received IVIG therapy regularly. After 6 months of treatment, most IVIG-treated subjects (91.7%) presented with muscular disease remission, compared to 55.6% of non-IVIG-treated subjects ( $p = 0.007$ ). During long-term IVIG treatment (up to 48 months), 16.7% of subjects presented with muscular relapses, which is significantly less than those who received no or only a few IVIG courses. The overall relapse-free period from any DM symptom was  $38.5 \pm 24.3$  months [Kampylafka, 2012].

SCIG has also been shown to be efficacious in treating subjects with DM/PM in smaller uncontrolled studies [Schleinitz et al, 2008; Danieli et al, 2011; Danieli et al, 2014; Gelardi et al, 2014; Cherin et al, 2016]. Long-term use of SCIG therapy has been described by Cherin [Cherin et al, 2016]. In doses of 1.9 g/kg monthly, 19 subjects were treated for a mean of 18.8 months. Median doses infused were 180 mL/week using 2 infusion pumps; similar to the infusion parameters in this study. Although these smaller studies have shown promising results, no large-scale or randomized controlled studies are available to corroborate the efficacy of SCIG against placebo in subjects with DM, which is a reason for the initiation of this study.

This study will build on previous evidence that has shown efficacy in the first 3 to 6 months of IgG treatment and will investigate whether the initial improvement can be sustained for 6 months to up to 7 years.

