### 3.4 Planned Study Duration

After up to 2 months of Screening, the duration for an individual subject is expected to be 24 weeks in Study Period 1 and 28 weeks in Study Period 2. The maximum study duration in the open-label Study Period 3 will be approximately 7 years; however, subject participation will end if the drug becomes commercially available or if there is no longer benefit from the study drug. For subjects not eligible to participate in Study Period 3, study duration will be up to 56 weeks (including the Follow-up Telephone Call).

See Section 3.7 for the definition of end of study.

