## 8.2 Blood Samples

During the study, blood will be taken from each subject for laboratory safety assessments, PK evaluations, ANA, MSA and MAA, exploratory biomarkers, and virology (HBV, HCV, and HIV) samples. Approximately 360.5 mL of blood will be drawn from each subject during Study Period 1 and Study Period 2. An additional 8 mL of blood per year of study participation will be collected during Study Period 3, with an additional 7.5 mL collected for virology retention at the EOP3 Visit, leading to a maximum of 392 mL collected over all 3 study periods. Detailed information on the volume of blood to be sampled for each assessment will be available in the ICF and laboratory manual.

Repeat or unscheduled blood samples may be taken for safety reasons or for technical issues with the samples and will be in addition to the estimated 392 mL blood volume for scheduled assessments.

Refer to the study manual for details about the collection, storage, handling and processing of blood samples.

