### 3 Purpose

This statistical analysis plan (SAP) provides a detailed and complete description of the planned statistical analyses for the following analyses to be presented in Clinical Study Reports (CSRs):

- primary data analysis of the study IgPro20\_3007 including all data collected during Study Period 1 (EOP1 analysis) will be done after all subjects have completed all assessments for Study Period 1
- at the time of the EOP1 analysis additional adverse event, efficacy data, and pharmacokinetic data of Study Period 2 will be analyzed. Efficacy analysis of the Study Period 2 data will be restricted to all subjects completing or discontinuing prematurely Study Period 2 at the time of data cut-off for the EOP1 analysis; the adverse events analysis will include all subjects treated in any study period at the time of data cut-off for EOP1 analysis; the pharmacokinetic analysis will include all subjects who have completed the rich PK sampling at Week 37. The respective analyses will be based on cleaned data.
- EOP2 analysis will be done after all subjects have completed all assessments for Study Period 2.
- EOP3 analysis will be done after all subjects have completed all assessments for Study Period 3.

Mock tables, listings, and figures shells are provided in separate supporting documents.

This SAP complies with the International Conference on Harmonisation (ICH) Harmonised Tripartite Guideline Topic E9, Statistical Principles for Clinical Trials. It is based upon the following study documents:

- Study Protocol Amendment 4, (dated 20 October 2022)

All decisions regarding the primary data analysis of the study results, as defined in this SAP document, must be made prior to unblinding of the study data.

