**Table 2: Study Objectives and Endpoints for Exploratory Endpoints**

Objectives	Endpoints
Exploratory: Study Period 1 and Study Period 2 (From Baseline to Week 53)	
• To assess pain / discomfort and anxiety / depression domains of EQ-5D-5L	• Pain / discomfort and anxiety / depression domains of EQ-5D-5L
• To assess Work Productivity and Activity Impairment Questionnaire for General Health (WPAI-GH)	• WPAI-GH
• To assess Abbreviated Treatment Satisfaction Questionnaire for Medication (TSQM-9)	• TSQM-9
• To assess Timed Up and Go result for functional ability to rise from a chair and ambulate	• Timed Up and Go
• To assess itch (pruritus)	• 5-Dimension (5-D) Itch (pruritus) score
• To assess muscle enzymes	• Creatine kinase (CK) • Lactate dehydrogenase (LDH) • Aspartate aminotransferase (AST) • Alanine aminotransferase (ALT) • Aldolase
• To assess the pharmacokinetics (PK) of IgG in Week 37	• Serum IgG PK parameters
• To assess antinuclear antibodies (ANA) and myositis-specific autoantibodies (MSA) and myositis-associated autoantibodies (MAA)	• ANA, MSA, and MAA
Exploratory: Study Period 3 (After Week 53)	
• To assess the efficacy of IgPro20 from after completion of Week 53 to the end of study participation	• Physician Global Disease Activity, Patient Global Activity Assessment, MMT-8, HAQ-DI, and CDASI from Baseline to EOP3
• To assess quality of life of IgPro20 from after completion of Week 53 to the end of study participation	• Mobility, Self-care, and Usual Activities domains of EuroQol 5-Dimension Questionnaire (EQ-5D-5L) from Baseline to EOP3
• Use of corticosteroid treatment from Week 53 to the end of study participation	• Reduction of average daily dose

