## 7.2 Treatment and Visit Descriptors

Period descriptions will show the weeks of interest, eg, Study Period 1 (Week 1 to 25), Study Period 2 (Week 25 to 53) or Study Period 3 (Week 53 to EOP3).

---

Sequence descriptions will display the respective treatment or treatment sequence.

The line displayed for visit “Baseline” comprises all baseline assessments as defined in Section [8.2.5](#), which is not necessarily identical to the summary of all assessments from the visit Baseline.

According to the protocol, for subjects who discontinue IMP early during participation in Study Period 1 or Study Period 2, all Week 53 assessments will be performed at the study visit where IMP treatment is discontinued instead of the assessments scheduled for that particular study visit. The Week 53 assessments will be assigned as follows:

- For subjects who discontinue IMP early in Study Period 1 -> EOT P1
- For subjects who discontinue IMP early in Study Period 2 -> EOT P2
- For subjects who do not discontinue IMP early in Study Period 1 or 2 -> Week 53

Analyses by visit will include for the EOT P1 visit the last assessment in Study Period 1 and for EOT P2 the last assessment in Study Period 2.

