### 8.2.26 Change of Oral Concomitant Corticosteroid Treatment

The change of oral concomitant corticosteroid treatment compares the average daily doses of the treatment in the reference week and the week of interest. The dose at week 1 (ie, the baseline dose) is the dose administered at the baseline date.

$$\begin{aligned} \text{average daily dose week X (mg*)} = \\ \text{sum of all daily doses of week X (mg*) / length week X (days)} \end{aligned}$$

If the length of a week is 0 (see Section 8.2.3) the respective average daily dose will be set to the average daily dose of the subsequent week with length > 0.

#### Change in Week X, for X=2 to 197

$$\begin{aligned} \text{change (\%)} = \\ 100 \times [(\text{average daily dose week X (mg*)} - \text{baseline dose (mg*)}) / \\ \text{baseline dose (mg*)}] \end{aligned}$$

\* mg prednisolone equivalent

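### Two figures do not fit a Study Period 3 of about 7 years: SAP 8.2.26 ends the corticosteroid change at Week 197, and the 392 mL blood maximum in Protocol 8.2 covers only 3 years

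*SAP*

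**What the plan says.** Protocol 3.4 states: "The maximum study duration in the open-label Study Period 3 will be approximately 7 years". The synopsis and the notes to the Period 1 and 2 schedule give the same length. Protocol 3.3.1 says that the study will "investigate whether the initial improvement can be sustained for 6 months to up to 7 years". The revision history lists, for Amendment 4, "Extend the study open-label period, Study Period 3, until" a point that is partly redacted in the public copy.

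The SAP names as its basis "Study Protocol Amendment 4, (dated 20 October 2022"). Its period descriptors (SAP 7.2) read "Study Period 3 (Week 53 to EOP3"), and its Table 9 also ends the period at EOP3. Neither sets a last week number. SAP Table 2 lists the exploratory objective "Use of corticosteroid treatment from Week 53 to the end of study participation", and SAP Table 13 gives the variable as the percent reduction of average daily dose, again without a week limit.

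The percent change itself is defined in SAP 8.2.26, under the line "Change in Week X, for X=2 to 197".

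Protocol 8.2 builds up the scheduled blood volume: about 360.5 mL in Periods 1 and 2, 8 mL for each year of Period 3, and 7.5 mL for virology retention at EOP3, "leading to a maximum of 392 mL collected over all 3 study periods". The next paragraph repeats 392 mL and says that repeat or unscheduled samples come on top of it.

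**The concern.** A derivation rule should cover every week in which a subject can contribute to the endpoint, and a figure called a maximum should cover the longest participation that the protocol allows. Week 197 and 392 mL do neither when set against about 7 years.

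The stakes are modest. If SAP 8.2.26 is followed literally, the long-term corticosteroid summary stops partway through the open-label period. If the programmers go past it, they depart from the written rule, and SAP 7 requires such deviations to be identified in the study report. For blood volume, the stated maximum for scheduled draws is too low for a subject who stays the whole time. A figure of this kind may also have been carried into documents that subjects see.

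**Working it through.** **Inputs**

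- Maximum length of Period 3: about 7 years (Protocol 3.4).
- Start of Period 3: Week 53 (SAP 7.2 and Table 9).
- Last week with a defined change: Week 197 (SAP 8.2.26).
- Visit spacing in Period 3: six months are counted as 24 weeks (Protocol 8.5.5.2). A year of 2 × 24 = 48 weeks is my inference from this. I also show 52-week years.
- Blood: 360.5 mL, 8 mL per year and 7.5 mL (Protocol 8.2).

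**Blood volume**

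With y years of Period 3, total = 360.5 + 8y + 7.5.

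- Reproducing the stated figure: 360.5 + 8 × 3 + 7.5 = 392 mL.
- Solving for y: (392 − 360.5 − 7.5) / 8 = 24 / 8 = 3.0 years.
- Leaving out the virology sample: (392 − 360.5) / 8 = 31.5 / 8 = 3.94 years. This reading does not reach 7 years either.
- At 7 years: 360.5 + 8 × 7 + 7.5 = 424 mL, which is 424 − 392 = 32 mL above the stated maximum.

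One item may be missing from this formula. Protocol Table 3 and Section 8.5.5.4 schedule hematology and biochemistry at EOP3 as well as at each End of Year visit, while the formula adds only the virology sample at EOP3. If EOP3 does not fall on an End of Year visit, there is one more draw. The documents do not give its volume. If it equalled the yearly 8 mL (an assumption), the total would be 424 + 8 = 432 mL.

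**Corticosteroid change**

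- Weeks of Period 3 covered: 197 − 53 = 144, or 144 / 4 = 36 four-week cycles.
- In years: 144 / 48 = 3.0, or 144 / 52 = 2.77.

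| Weeks per year | Week at 7 years | Weeks after Week 197 | Share of a 7-year Period 3 |
|---|---|---|---|
| 48 | 53 + 7 × 48 = 389 | 389 − 197 = 192 | 192 / 336 = 57% |
| 52 | 53 + 7 × 52 = 417 | 417 − 197 = 220 | 220 / 364 = 60% |

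Neither year length brings Week 197 near the end of a 7-year period.

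**The case against.** The strongest reply is that this is a leftover of little consequence, and much of that reply stands.

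- **Carry-through.** A reader might infer that the 7-year length was not carried through the documents in general. They do not support that. The synopsis, the schedule notes and Protocol 3.3.1 and 3.4 all give 7 years, and the SAP's period definitions are open-ended. The mismatch is confined to one line in SAP 8.2.26 and the volumes in Protocol 8.2.
- **Lost data.** A reader might also infer that data after Week 197 are discarded. The line limits one derived variable and excludes nothing that is collected. The objective and Table 13 have no week limit, and SAP 8.2 refers to separate dataset specifications for full derivation details. The endpoint is exploratory and descriptive.
- **Share of follow-up.** The 57% to 60% applies only to a subject who stays the full 7 years. Participation can end sooner, on commercial availability or loss of benefit, and the documents give no expected duration. The share of actual data affected is unknown.
- **Origin.** Both figures fit a 3-year Period 3, but no current text states one, and the relevant amendment wording is partly redacted. For Week 197 the fit also needs a 48-week year. The mismatch with about 7 years does not depend on this history.
- **Blood volume.** The 360.5 mL is approximate, the 392 mL is also called an estimate, and the section refers to the consent form and laboratory manual for detail. I have not seen either, so no error in them can be claimed.

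Two things remain after all this. The rule in SAP 8.2.26 stops before the endpoint does, and a volume labelled as a maximum for scheduled draws does not cover the longest permitted participation.

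**Conclusion.** The point holds as an inconsistency between two figures and the current maximum length of Study Period 3. It is minor and worth correcting.

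- SAP 8.2.26 leaves the Period 3 corticosteroid change undefined after Week 197. For a subject who completes 7 years, that is about 190 to 220 weeks, depending on whether years are counted as 48 or 52 weeks.
- The 392 mL in Protocol 8.2 is correct arithmetic for 3 years. For 7 years the same formula gives about 424 mL. That figure assumes 8 mL in each of exactly 7 years and no separate safety draw at EOP3, so it should not be read as a firm ceiling.

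The primary and key secondary analyses use Study Period 1 data only and are untouched.

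**What to change.** In SAP 8.2.26, replace the fixed upper limit of 197 by the last week of Study Period 3 (EOP3). This matches the SAP's own period definitions and needs no further change if the length of Period 3 changes. Check that the dataset specifications use the same limit.

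In Protocol 8.2, restate both mentions of 392 mL. Either give about 424 mL for 7 years, or give the components: 360.5 mL, plus 8 mL per year of Period 3, plus the samples taken at EOP3. The second form is safer, because the length is approximate and the EOP3 draw may be separate. Check the volumes against the laboratory manual and consent form first.

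The cost is a small SAP edit, which can be made well before the EOP3 analysis, and a slightly larger stated blood volume. The protocol text change goes through the usual notification or approval route (Protocol 13.3). If the consent form carries the same figure, whether it needs revision falls under Protocol 12.3. No data collection or analysis method changes.

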### 8.2.27 Oral Rescue Corticosteroid Treatment

Oral Rescue Corticosteroid Treatment will be identified via the rescue flag as documented on the ‘Oral Corticosteroid Treatment CRF’. Rescue Medication prior to Week 9 is a protocol deviation.

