## 5.3 Other Interventions

### 5.3.1 Oral Rescue Corticosteroid Treatment

In the event of clinical worsening (eg, subject meets DOW criteria) between Week 9 and Week 25, the investigator may decide that the subject requires oral rescue corticosteroid treatment for recovery. Intravenous pulse rescue corticosteroid treatment is not permitted.

In this case, the following guidance applies:

- 1 Oral rescue corticosteroid treatment should be given only if DOW criteria are met.
- 2 The earliest that oral rescue corticosteroid treatment can be given is Week 9, to allow for IMP steady state to be achieved. The DOW consists of meeting 1 of the following 3 criteria on 2 consecutive study visits at least 2 weeks apart, up to Week 25:

- a) Physician Global Disease Activity Assessment VAS worsening  $\geq 2$  cm\* and MMT-8 worsening  $\geq$  absolute 10%, - OR -
- b) Extramuscular Global Assessment VAS worsening  $\geq 2$  cm, - OR -
- c) Any 3 of 6 CSMs (see [Section 3.3.1](#)) worsening by  $\geq$  absolute 20%
  - \* If baseline Physician Global VAS is 8 to 10, then any worsening on Physician Global VAS is acceptable as long as MMT-8 criterion is met.

3 The rescue oral corticosteroid (prednisolone equivalent) treatment should be provided as per the Treating Physician's (see [Table 7](#)) standard of care but should not exceed 1 mg/kg/day for up to 5 days.

4 It is recommended that after oral rescue corticosteroid treatment, the oral corticosteroid dose be returned to Baseline dose by Week 25, if clinically possible.

Clinical worsening according to DOW is finished at the first subsequent study visit where none of the criteria are met. A potential next DOW and possible rescue oral corticosteroid treatment can start only after the end of the preceding DOW.

Oral rescue corticosteroid treatment is not permitted in Study Period 2. During Study Period 3, the use of additional oral corticosteroid treatment is permitted. Prior to increasing corticosteroids, investigators should verify that subjects are still benefiting from treatment with IgPro20.

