## 7.3 Prohibited Therapies

The following therapies are NOT PERMITTED during the study and require a minimum washout period (in parentheses) before Baseline if discontinued:

- IM, IV, or intra-articular corticosteroids including adrenocorticotropic hormone (1 month)
- IgG (up to 2 months [Note: Subject may enroll before the end of the 2 month washout period if clinical deterioration is experienced after withdrawal of IgG.])
- Plasma exchange or plasmapheresis (3 months)
- Cyclophosphamide or alkylating agents (6 months)
- Other biologic therapies including investigational agents (6 months or 5 half-lives, whichever is longer)
- Rituximab or other B cell depleting therapies (9 months or evidence of persistent B cell depletion after stopping therapy)

Subjects will not be enrolled into the study if they receive any prohibited therapy or any therapy in a prohibited dosage that cannot be discontinued or reduced to a permitted dose before Baseline.

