**Table 3: Assumptions for Power Analysis**

Treatment Sequence A	Probability of having a TIS $\geq 20$ points at Week 17	Probability of having a TIS $\geq 20$ points at Week 21	Probability of having a TIS $\geq 20$ points at Week 25
A	65%	90%, if TIS $\geq 20$ points at Week 17	90%, if TIS $\geq 20$ points at Week 21
		20%, if TIS $< 20$ points at Week 17, or withdraw, or receive oral rescue corticosteroid treatment before Week 17	20%, if TIS $< 20$ points at Week 21, or withdraw, or receive oral rescue corticosteroid treatment before Week 21
B	30%	90%, if TIS $\geq 20$ points at Week 17	90%, if TIS $\geq 20$ points at Week 21
		10%, if TIS $< 20$ points at Week 17, or withdraw, or receive oral rescue corticosteroid treatment before Week 17	10%, if TIS $< 20$ points at Week 21, or withdraw, or receive oral rescue corticosteroid treatment before Week 21

A Treatment sequence A = 0.5 g/kg IgPro20 for 24 weeks followed by 0.5 g/kg IgPro20 for 28 weeks; Treatment sequence B = placebo for 24 weeks followed by 0.5 g/kg IgPro20 for 28 weeks.

Simulation shows a total of 126 subjects (63 subjects per treatment sequence) will be required for a power of 90% in 1-sided Fisher's exact test at a significance level of 0.025. Fisher's exact test is used in the power simulation as a close approximation to the exact logistic regression model in the primary endpoint analysis.

For further details see [Appendix 14.1](#).

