### 10.1 Primary Estimand

The primary interest is to quantify the treatment effect of IgPro20

- where the potential confounding effect of oral rescue corticosteroid treatment is excluded
- where the potential confounding of subjects who withdraw from treatment or the study before Week 25 and cannot provide sufficient data to demonstrate a benefit of treatment is excluded, and
- in the absence of premature withdrawal from IMP or the study before Week 25 due to the Ukraine war [[EMA Biostatistics Working Party, 2022](#); [ICH E9 \(R1\), 2020](#)].

The primary estimand in line with the primary interest of the study is described as follows:

- Population: the target patient population defined by eligibility criteria and who received any amount of randomized IMP and have post baseline efficacy results in Study Period 1 (mITT). See Section 6 for details.
- Variable: responder status based on TIS assessments at Weeks 17, 21, and 25
- Intercurrent events:
  - withdrawal from randomized IMP or the study, which is not related to the Ukraine war, or receiving oral rescue corticosteroid treatment before Week 25 is considered treatment failure
  - withdrawal from randomized IMP or the study which is related to the Ukraine war will be addressed using the hypothetical strategy [Meyer et al, 2020; Collins et al, 2020].
- Population-level summary: responder rate by treatment sequence

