## 10.2 Analysis of Primary Endpoint

The primary endpoint is the responder status in each treatment sequence based on TIS assessments at Weeks 17, 21, and 25. Following the estimand described in Section 10.1, a responder is defined as a subject with a TIS  $\geq 20$  points at Week 25 and at least at 1 of the previous scheduled visits (Week 17 or Week 21) who completes 24 weeks of randomized IMP treatment without the use of oral rescue corticosteroid treatment.

Therefore, for subjects who do not withdraw from IMP or the study for reasons which are related to the Ukraine war before Week 25, non-responders will include subjects who meet any 1 of the following:

- TIS  $< 20$  points at Week 25
- TIS  $< 20$  points at both Weeks 17 and 21
- Withdraw from treatment or the study or receive oral rescue corticosteroid treatment before Week 25 (Note: for subjects with corticosteroid taper starting at Week 17, only an increase to doses greater than 125% of the Baseline corticosteroid dose following corticosteroid taper starting at Week 17 will be considered a “rescue” corticosteroid dose)

To ensure that the treatment effect is not confounded by the intercurrent event of premature withdrawal from IMP or the study due to the Ukraine war, the hypothetical strategy is applied for this intercurrent event to quantify the treatment effect in the absence of the Ukraine war [Meyer et al, 2020; Collins et al, 2020]. For subjects who withdraw from IMP or the study for reasons which are related to the Ukraine war before Week 25, scheduled TIS assessments after withdrawal are missing. These missing values can be considered missing at random (MAR) and multiple imputation will be used to derive the hypothetical post-intercurrent event TIS values and the corresponding response variables assuming that the subjects with missing TIS values continue in the same way as similar subjects in the study who did not withdraw prematurely. Multiple imputation is a simulation based approach where missing values are replaced by multiple Bayesian draws from the conditional distribution of missing data given the observed data and covariates, creating multiple completed data sets. The completed data sets can then be analyzed using standard methods. Note: If no TIS values are available for the subject for any post-randomization visit during Study Period 1, the subject will be excluded from the mITT analysis set (see Section 6).

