**Table 14: Results of Sample Size Simulation**

Total sample size	Probability of TIS $\geq 20$ conditional on showing a response at the previous visit	Power	Estimated median responder rate in Treatment Sequence A	Estimated median responder rate in Treatment Sequence B
116	0.95	0.914	0.655	0.345
	0.9	0.855	0.603	0.310
	0.85	0.784	0.552	0.276
118	0.95	0.925	0.661	0.339
	0.9	0.869	0.610	0.305
	0.85	0.806	0.542	0.271
120	0.95	0.933	0.667	0.333
	0.9	0.878	0.600	0.300
	0.85	0.817	0.550	0.283
122	0.95	0.932	0.656	0.344
	0.9	0.882	0.607	0.311
	0.85	0.821	0.557	0.279
124	0.95	0.939	0.661	0.339
	0.9	0.895	0.597	0.306
	0.85	0.833	0.548	0.274
126	0.95	0.948	0.667	0.333
	0.9	0.905	0.603	0.317
	0.85	0.839	0.556	0.286
128	0.95	0.934	0.656	0.344
	0.9	0.887	0.609	0.313
	0.85	0.844	0.547	0.281
130	0.95	0.940	0.662	0.338
	0.9	0.897	0.600	0.308
	0.85	0.847	0.554	0.277

The total sample size of 126 subjects is selected as the minimum sample size for a power of  $\geq 90\%$  based on the above assumptions.

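### Starting a prohibited systemic dermatomyositis therapy before Week 25 is not a failure event in the primary estimand, and the rescue flag and the 125% dose rule have no stated precedence

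*SAP*

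**What the plan says.** **Failure events.** SAP 10.1 lists withdrawal unrelated to the Ukraine war, "or receiving oral rescue corticosteroid treatment before Week 25 is considered treatment failure". The non-responder list in SAP 10.2 repeats these two events and adds only the TIS criteria. SAP 10.3 and 10.4 remove MMRM data after oral rescue or after withdrawal from randomized treatment, and after nothing else.

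**Prohibited therapy.** Protocol 7.3 opens with "The following therapies are NOT PERMITTED during the study". It lists IM, IV and intra-articular corticosteroids, IgG, plasma exchange, cyclophosphamide, other biologics and rituximab. Protocol 5.3.1 adds: "Intravenous pulse rescue corticosteroid treatment is not permitted". Neither section states a consequence for the endpoint. Use of such a therapy is not on the mandatory discontinuation list in Protocol 4.3.1.

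**Rescue classification.** SAP 8.2.27 says that oral rescue "will be identified via the rescue flag as documented on the" oral corticosteroid form. SAP 10.2, following Protocol 5.3.2, says that for subjects who taper from Week 17, "only an increase to doses greater than 125% of the Baseline corticosteroid dose following corticosteroid taper starting at Week 17 will be considered" rescue. Protocol 5.3.1 and Table 7 also make rescue conditional on the Definition of Worsening (DOW).

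**The concern.** The estimand says that it measures the treatment effect with the confounding effect of rescue excluded. An oral corticosteroid course given for a flare makes the subject a non-responder. A prohibited and possibly stronger treatment for the same flare, such as IV corticosteroid or IgG, does not. Any improvement it produces is credited to the randomized arm, both in the responder count and in the continuous key secondary endpoints.

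The rescue question is narrower. Where the recorded flag and the recorded dose disagree, two readers of the SAP could classify the same subject differently. That classification decides responder status and who enters the imputation data sets (10.2). It also decides where MMRM data stop (10.4), the corticosteroid-reduction endpoint (10.3), time-to-event censoring (10.5) and the post-discontinuation window (8.2.3).

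**Working it through.** **1. Can such a subject be a responder?** Take a subject who starts a Protocol 7.3 therapy for DM at, say, Week 15.

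- Mandatory discontinuation (Protocol 4.3.1): not triggered by this event.
- Forced withdrawal (Protocol 8.4): applies to prohibited dose adjustments of *permitted* therapies. Starting a prohibited one is not covered.
- Oral rescue (SAP 8.2.27): no oral rescue, so no flag.
- 125% rule (SAP 10.2): concerns the corticosteroid dose after a Week 17 taper, so it does not reach IgG, plasma exchange or a biologic.

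If the subject completes 24 weeks of treatment with TIS ≥ 20 at Week 25 and at Week 17 or 21, the SAP returns "responder". No MMRM value is removed.

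**2. Reproduce the planning figure.** Inputs from SAP 4.5 and 14.1:

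- Week 17 response r = 0.65 (IgPro20) and 0.30 (placebo).
- Response given response at the previous visit, c = 0.90.
- Response given non-response at the previous visit, q = 0.20 (IgPro20) and 0.10 (placebo).
- 63 subjects per arm; one-sided Fisher's "exact test at a significance level of 0.025".

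Responder rate = r·c² + r(1−c)q + (1−r)q·c

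- IgPro20: 0.65×0.81 + 0.65×0.10×0.20 + 0.35×0.20×0.90 = 0.5265 + 0.0130 + 0.0630 = 0.6025
- Placebo: 0.30×0.81 + 0.30×0.10×0.10 + 0.70×0.10×0.90 = 0.2430 + 0.0030 + 0.0630 = 0.3090

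Exact power is the sum of the binomial probabilities over all tables with one-sided p < 0.025. It is 0.904, against 90% in SAP 4.5 and 0.905 simulated in Table 14. The plan's figure reproduces.

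**3. Effect of misclassified subjects (assumed counts).** The documents give no rate of prohibited-therapy use or of flag and dose disagreement, so k = 1, 2, 3 is an illustration. Each k raises the rate of the affected arm by k/63. Type I error takes both true rates as 0.309.

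| k | Placebo rate, if placebo only | Power, placebo only | Power, k in both arms | One-sided type I error, IgPro20 only |
|---|---|---|---|---|
| 0 | 0.309 | 0.904 | 0.904 | 0.016 |
| 1 | 0.325 | 0.867 | 0.903 | 0.026 |
| 2 | 0.341 | 0.822 | 0.903 | 0.039 |
| 3 | 0.357 | 0.770 | 0.903 | 0.058 |

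**4. Sensitivity to one subject.** With 31 against 19 responders of 63, one-sided p = 0.0223. With 30 against 19 it is 0.0336, and with 31 against 20 it is 0.0345. Near the boundary, one classification decides the trial.

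Fisher's test stands in here for the exact logistic regression with multiple imputation, as it does in the plan's own power calculation.

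**The case against.** **A reader might infer that the SAP holds two contradictory definitions of rescue.** The documents do not go that far. The flag can be read as the data source and the 125% rule as the definition that sites apply when they set it. The dose rule also covers only subjects who tapered from Week 17. A conflict arises only where recorded flag and dose disagree. What stands is that no precedence and no cross-check are stated.

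**A reader might infer that flare treatment outside the rescue rules never counts as failure.** For oral corticosteroids there is a route. Protocol 7.2 allows almost no change to permitted therapy in Study Periods 1 and 2, Protocol 8.4 makes prohibited adjustments lead to withdrawal from treatment, and Protocol 4.3.5 makes withdrawal before Week 25 non-response. An unflagged oral increase should therefore end as failure if sites apply 8.4. That route does not reach the start of a Protocol 7.3 therapy. Noncompliance (Protocol 4.3.1) and withdrawal for deviations (Protocol 13.4) could reach it, but they rest on judgement.

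**The plan has mitigations.** The primary and key secondary analyses are repeated on the per-protocol set, with violations defined at the blinded data review meeting (BDRM). That analysis is only supportive. Sensitivity analysis (5) in SAP 10.2.1 concerns increased oral corticosteroids without DOW. It is a title with no algorithm, and it covers oral use only.

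**The event may be rare.** The subject must receive a forbidden drug, not be withdrawn, and meet the TIS criteria at two visits. Protocol 3.3.1 does not expect many flares that meet DOW. This bears on size, not on the missing rule.

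**Conclusion.** The gap is real. Following the SAP as written, a subject who starts a prohibited systemic therapy for DM before Week 25 and stays on study drug can be a responder, with later values kept in the MMRM. That contradicts the estimand's stated aim. The missing precedence between flag and dose is a smaller, secondary defect.

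Its size is not known, because the documents give no frequency. One might infer that the error shrinks the observed effect, since flares could be expected more often on placebo. The documents do not establish this. Placebo-only misclassification costs power, equal counts leave it almost unchanged, and IgPro20-only misclassification inflates type I error above 0.025 from the first subject. The figures for 1 to 3 subjects rest on assumed counts and on the planning rates. They show that a few cases could matter in either direction, not that they will occur. The sample size calculation itself is not in question.

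**What to change.** Make these changes before unblinding for the primary data analysis:

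1. **SAP 10.1 and 10.2.** Add the start of a Protocol 7.3 systemic therapy given for DM before Week 25 as an intercurrent event handled as treatment failure, like oral rescue. Composite failure is one of several possible strategies; it is chosen here to match the existing treatment of rescue.
2. **SAP 10.3 and 10.4.** Set MMRM values after that event to missing, as already done after oral rescue.
3. **Identification.** Find cases from coded concomitant medication, with blinded review of the indication at the BDRM. Protocol 7.3 lists drugs regardless of indication, so use for an unrelated condition, such as intra-articular corticosteroid for a joint problem, should not count.
4. **SAP 8.2.27 and 10.2.** Write one rescue derivation that uses the flag together with the recorded dose. State which governs when they disagree, and produce a blinded discrepancy listing for the BDRM. SAP 8.2.26 already derives average daily doses in prednisolone equivalents.
5. **SAP 10.2.1.** Give sensitivity analysis (5) an algorithm.

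Protocol 4.3.1, 5.3.1, 5.3.2, 7.3 and 8.4 must be reconciled on the consequence of prohibited therapy and of corticosteroid increases. No dose or clinical rule is proposed here.

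The cost is SAP wording, derivation from data already collected, and a small blinded review. The downside is that a few more subjects in either arm may count as non-responders.
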